### 11.5 Record Retention

The Sponsor and Investigator/Site will archive and retain all documents pertaining to the clinical investigation as per the applicable regulatory record retention requirements. The Investigator must obtain permission from Sponsor in writing before destroying or transferring control of any clinical investigation records.

### 11.6 Investigational Devices Accountability

The Sponsor ships investigational products only to the Principal Investigator (the responsible leader of the investigational site) or his/her legal designee of each site, after sites receive documentation of site activation and shipping authorization is complete.

The Investigator or an authorized designee must maintain adequate records of the receipt and disposition of each investigational device, including part number, batch number, and serial number (if applicable), date used, subject identification, and treating physician. See **Table 1** for a listing of investigational devices by geographic location.

Storage locations for the devices at investigational sites must be locked with access restricted only to investigators and authorized personnel.

Inventory Accountability Log supplied by the Sponsor will be used. The Inventory Accountability Log must document the disposition of all investigational devices including those that have been returned to Sponsor.

All investigational devices that are associated with a device failure or device deficiency must be returned immediately to the Sponsor.

## 12.0 ETHICAL CONSIDERATION

### 12.1 Institutional Review Board/Medical Ethics Committee Review and Approval

Institutional Review Board (IRB)/ Ethics Committee (EC) approval for the CIP and ICF/other written information provided to the patient will be obtained by the Principal Investigator at each investigational site prior to consenting and enrolling patients in this clinical investigation. The approval letter must be received prior to the start of this clinical investigation and a copy must be provided to the Sponsor.

Any amendments to the CIP as well as associated ICF changes will be submitted to the IRB/EC and written approval obtained prior to implementation, according to each institution's IRB/EC requirements.

No changes will be made to the CIP or ICF or other written information provided to the patient without appropriate approvals, including IRB/EC, the Sponsor, and the regulatory agencies (if applicable).

Until the clinical investigation is completed, the Investigator will advise his/her IRB/EC of the progress of this clinical investigation, per IRB/EC requirements. Written approval must be obtained from the IRB/EC yearly to continue the clinical investigation, or according to each institution's IRB/EC requirements.

## Clinical Investigation Plan

No investigative procedures other than those defined in this CIP will be undertaken on the enrolled subjects without the written agreement of the IRB/EC and the Sponsor.

### **13.0 CLINICAL INVESTIGATION CONCLUSION**

The clinical investigation will be concluded when:

- All sites are closed AND
- The final report has been provided to investigators or the Sponsor has provided formal documentation of clinical investigation closure. The final report will be submitted no later than 1-year following the date on which all subjects have either completed the last scheduled follow-up visit or withdrawn from the study.

### **14.0 PUBLICATION POLICY**

The data and results from the clinical investigation are the sole property of the Sponsor. The Sponsor shall have the right to access and use all data and results generated during the clinical investigation. The Investigators will not use this clinical investigation-related data without the written consent of the Sponsor for any purpose other than for clinical investigation completion or for generation of publication materials, as referenced in the Clinical Trial Agreement. Single-center results are not allowed to be published or presented before the multi-center results. Any proposals for publications or presentations by the investigators must be reviewed and approved by the Sponsor in a timely manner to enable Sponsor review in compliance with the Sponsor's publication policy set forth in the Clinical Trial Agreement.

Upon receiving IDE approval from the FDA, the Sponsor will be responsible for registering this clinical investigation on [www.clinicaltrials.gov](http://www.clinicaltrials.gov) or any other clinical trials, in accordance with the International Committee of Medical Journal Editors guidelines, or any other applicable guidelines. Sponsor shall be responsible for any such registration and results posting as required by the ClinicalTrials.gov website. Institution and/or Principal Investigator(s) shall not take any action to register the clinical investigation. A full report of the pre-specified outcomes, regardless of the results, will be made public through the ClinicalTrials.gov website no later than 12 months after clinical investigation completion, as required by section 801 of the FDA Amendments Act. If this clinical investigation is terminated early, the Sponsor will make every effort to hasten the release of the pre-specified outcomes through the ClinicalTrials.gov website.

### **15.0 RISK ANALYSIS**

Risks associated with the TactiFlex SE ablation catheter and EnSite IDE Display Workstation are managed in accordance with ISO 14971. The risk analyses for these devices included objective reviews of published and available unpublished medical and scientific data. The sections below provide an overview of residual risks identified in the risk management reports and anticipated benefits of the medical devices. The additional tests and assessments required by the clinical investigation were analyzed for additional risks and are incorporated in the sections below.

#### **15.1 Anticipated Clinical Benefits**

The intended clinical benefit of the TactiFlex™ Ablation Catheter, Sensor-Enabled™ is to provide relief of drug refractory recurrent symptomatic paroxysmal atrial fibrillation.

## Clinical Investigation Plan

While there is no guaranteed clinical benefit associated with participation in this study, it is expected that TactiFlex SE will have similar benefits as other commercially available ablation catheters in maintaining sinus rhythm. The clinical benefits of sinus rhythm are well established and include relief of symptoms and improvements in exercise tolerance, hemodynamics, LV function, and quality of life. Restoration of sinus rhythm may confer a mortality benefit.

The EnSite IDE Display Workstation clinical benefits include the diagnosing of complex arrhythmias in cardiac patients as well as mapping prior to the implantation of electrical devices, catheter ablation or surgical ablation, and for the guiding of antiarrhythmic drug-therapy. Compared to the market-released EnSite Velocity v5.2.1 / Ensite Precision v2.2 software, no new labeled or performance claims are being targeted as part of the Precision v2.5 IDE Software release.

The information gathered from this study will also add to the understanding of the treatment options for subjects with paroxysmal AF. This knowledge may advance medical science and have a benefit on other subjects with a similar arrhythmia.

### 15.2 Foreseeable Adverse Events and Anticipated Adverse Device Effects

Risks associated with the TactiFlex SE ablation catheter and the EnSite IDE Display Workstation, and the EP procedure, together with their likely incidence, are described in the Investigator's Brochure. There may be risks related to the device under investigation that are unknown at present. Likewise, the exact frequency of the risk may be unknown.

The following is a list of foreseeable adverse events and anticipated adverse device effects:

- Abnormal vision
- Anesthesia reaction
- Angina/chest pain/discomfort
- Aorto-right atrial fistula
- Arrhythmia, including exacerbation of pre-existing atrial fibrillation
- Arteriovenous fistula
- Bleeding, including major bleeding requiring surgery or transfusion/hematomas/anemia
- Cardiac tamponade
- Cardiovascular injury, including atrial trauma and cardiac perforation
- Coagulation
- Component damage to ICD or implantable pacemaker
- Coronary artery spasm
- Cough
- Cytotoxicity/systemic toxicity/sensitization/endotoxin/pyrogen
- Death
- Dislodgement of implantable cardioverter defibrillator or pacing leads
- Dissection, vessel, coronary artery/pulmonary vein
- Disseminated intravascular coagulation
- Effusion, pericardial
- Effusion, pleural
- Electrical shock/injury
- Elevated cardiac enzymes
- Embolism, air/cardiac/pulmonary/pulmonary vein
- Embolism, material/component
- Endocarditis

## Clinical Investigation Plan

- Exacerbation of chronic obstructive pulmonary disease (COPD)
- Fever
- Heart block
- Heart failure
- Hypotension
- Immunological reaction, including anaphylaxis
- Infection
- Laceration
- Left atrial esophageal fistula
- Myocardial infarction
- Organ injury
- Pain, neck/back/groin
- Palpitations
- Pericarditis
- Phrenic nerve injury/diaphragmatic paralysis
- Pneumonia
- Pneumothorax/hemothorax
- Pseudoaneurysm
- Pulmonary edema
- Pulmonary hypertension
- Radiation injury
- Respiratory failure/distress/depression/hypoxia
- Seizure
- Sepsis
- Severe pulmonary vein (PV) stenosis (>70%), or complete occlusion of a PV
- Shock
- Skin burns
- Stiff Left Atrial Syndrome
- Stroke/cerebrovascular accident
- Syncope/vasovagal reaction/dizziness
- Thromboembolism
- Thrombus, including coronary artery/vessel occlusion
- Tissue charring
- Transient ischemic attack (TIA)
- Unintended ablation
- Vagal nerve injury/Gastroparesis
- Valvular damage or insufficiency
- Vessel wall damage
- Volume overload

### 15.3 Residual Risks Associated with the Device Under Investigation, as Identified in the Risk Analysis Report

Risk analyses for the TactiFlex SE ablation catheter and the EnSite IDE Display Workstation were performed based on risk management plans. The risk analysis process utilizes Failure Mode Effect Analysis (FMEA) tools to systematically identify potential hazards associated with the design and use of the device. Based upon the pre-clinical and bench-testing data for TactiFlex SE and EnSite IDE Display

## Clinical Investigation Plan

Workstation, along with clinical data for similar catheter designs (with either contact-force sensing or flexible tips) and market-released EnSite Velocity v5.2.1 / Ensite Precision v2.2 software, all identified residual risks are determined to be within acceptable levels.

The overall residual risk is acceptable given the individual risks are acceptable and the overall benefits outweigh the overall risks.

### 15.4 Risks Associated with Participation in this Clinical Investigation

Possible risks associated with participating in this clinical study are not anticipated to be any different from risks associated with undergoing procedures with commercially available open-irrigated contact force-sensing RF ablation catheters with electro-anatomical mapping systems. Protocol required assessments are summarized in **Section 6.6.7**. These assessments are standard of care for TactiFlex SE and as such do not pose any additional risks.

### 15.5 Possible Interactions with Protocol-Required Concomitant Medications

There are no known interactions with concomitant treatments.

### 15.6 Steps Taken to Control or Mitigate Risks

In-depth recommendations, special precautions and instructions regarding patient selection, device handling, and device placement are included in the IFU for TactiFlex SE. It is also stated in the IFU that the devices can only be used by physicians who have received appropriate training on how to use the device. This statement is interpreted to mean that the physician users are expected to be aware of the known and foreseeable safety risks associated with the use of the device including the surgical and/or non-surgical treatment of these conditions.

Risks associated with the use of the devices under investigation are minimized through device design, investigator selection and training, pre-specified patient eligibility requirements, and study monitoring to ensure adherence to the protocol. All adverse events will be reported to the Sponsor as summarized in **Section 7.3** and will be monitored internally for safety surveillance purposes.

**Device Design:** The TactiFlex SE catheter has a contact force sensor which plays an important factor in achieving transmural lesions that is critical in abolishing the substrate necessary for an arrhythmia and AF in particular. With increasing force, a greater proportion of the electrode surface area is in contact with the tissue, and there is more efficient energy coupling. Gaps in ablation lines are commonly seen when the amount of contact force over the RF delivery time is low and this is associated with higher recurrence rates after ablation for AF. Contact force-sensing ablation catheters such as TactiFlex SE provide a valuable feedback mechanism to help ensure the efficacy of ablation.

TactiFlex SE also utilizes a flexible electrode tip design that has been shown in pre-clinical testing without a contact force sensor [25] to have a lower risk of steam pops during ablation compared to competitive devices. The position of the thermocouple in the flexible tip electrode provides valuable feedback to improve safety.

The catheter also has a magnetic sensor that provides position and orientation information about the catheter to provide information about the direction and magnitude of applied force to the catheter tip electrode and the deflection plane of the catheter. This information is helpful to an operator as they navigate the device in the anatomy. The EnSite IDE Display Workstation has a modified graphical user interface (GUI) that enables the operator to visualize position, orientation, contact force and deflection direction information provided by the catheter's magnetic sensor.

## Clinical Investigation Plan

**Investigator Selection and Training:** Investigators will be selected as outlined in **Section 10.1**. Sites will receive training as stated in **Section 10.4.1**. Additionally, ablating physicians will be qualified and have experience using a contact force sensor as stated in **Section 10.4.2**.

**Adherence to the Clinical Investigational Protocol:** The clinical study will be monitored by the Sponsor to ensure adherence to the CIP. Subjects will be carefully selected through rigorous screening using pre-specified inclusion and exclusion criteria as stated in **Section 5.2**. Adverse events will be reported to the Sponsor and will be monitored internally for safety surveillance purposes and reported to regulatory authorities as applicable. Adverse events will be adjudicated by qualified physicians who are not participating in the study.

### 15.7 Risk to Benefit Rationale

Extensive risk analysis and risk mitigation plans (as summarized in **Section 15.3**) has been implemented to minimize any residual risk of the TactiFlex SE catheter and EnSite IDE Display Workstation to subjects. Treatment with TactiFlex SE has all the benefits of a state-of-the-art cardiac ablation therapy with the added benefits of being able to monitor contact force at the catheter tip. The EnSite IDE Workstation has all the benefits of a state-of-the-art electro-anatomical mapping system, while enabling the use of TactiFlex SE for cardiac mapping and ablation procedures. The residual risks are outweighed by the anticipated benefits, as described in the previous sections, and the overall risk has been determined to be acceptable.

## Clinical Investigation Plan

### APPENDIX I: ABBREVIATIONS AND ACRONYMS

Acronym/Abbreviation	Description
AAD	Antiarrhythmic drug
ACC	American College of Cardiology
ADE	Adverse device effect
AE	Adverse event
AF	Atrial fibrillation
AFEQT	Atrial Fibrillation Effect on QualiTY of Life
AFL	Atrial flutter
APHRS	Asia Pacific Heart Rhythm Society
AT	Atrial tachycardia
CEC	Clinical Events Committee
CF	Contract force
CFAE	Complex fractionated atrial electrograms
CFR	Code of Federal Regulations (US)
CIP	Clinical investigation plan
CRF	Case report form
CT	Computed tomography
CTI	Cavotricuspid isthmus
CVA	Cerebrovascular accident
DMP	Data Management Plan
DSMB	Data Safety Monitoring Board
EC	Ethics Committee
ECAS	European Cardiac Arrhythmia Society
ECG	Electrocardiogram
EDC	Electronic data capture
EHRA	European Heart Rhythm Association
EMEA	Europe, the Middle East and Africa
EQ	EuroQol Group
ESC	European Society of Cardiology
EU	The European Union
FDA	Food and Drug Administration
GCP	Good Clinical Practice
GUI	Graphical user interface
HIPAA	Health Insurance and Portability and Accountability Act
HRS	Heart Rhythm Society
HSP	High standard power (40-50 Watts)
ICE	Intracardiac echocardiography
ICD	Implantable cardioverter defibrillator
ICF	Informed consent form
ICM	Implantable cardiac monitor
IDE	Investigational device exemption
IFU	Instructions for use
ILR	Implantable loop recorder
INR	International normalized ratio

## Clinical Investigation Plan

Acronym/Abbreviation	Description
IRB	Institutional Review Board
ISO	International Standards Organization
LAA	Left atrial appendage
LAD	Left atrial diameter
LCD	Liquid crystal display
LVEF	Left ventricular ejection fraction
MHRA	Medicines & Healthcare products Regulatory Agency (United Kingdom)
MI	Myocardial infarction
MRI	Magnetic resonance imaging
NIH	National Institutes of Health
NIHSS	National Institutes of Health Stroke Scale
NOAC	Novel oral anticoagulant
NYHA	New York Heart Association
OUS	Outside of the US
PAF	Paroxysmal atrial fibrillation
PCI	Percutaneous coronary intervention
PG	Performance goal
PMA	Pre-market approval
PMDA	Pharmaceuticals and Medical Devices Agency (Japan)
PP	Per protocol analysis population
PTE	Per treatment evaluable
PV	Pulmonary vein
RF	Radiofrequency
SADE	Serious adverse device effect
SAE	Serious adverse event
SE	Sensor enabled
SOLAECE	Latin America Society of Electrophysiology and Cardiac Stimulation
SVT	Supraventricular tachycardia
TEE	Transesophageal echocardiogram
TIA	Transient ischemic attack
TTE	Transthoracic echocardiogram
TTM	Transtelephonic monitoring
UADE	Unanticipated adverse device effect
USADE	Unanticipated serious adverse device effect
US	United States of America
WW	Worldwide

## Clinical Investigation Plan

### APPENDIX II: DEFINITIONS

The following definitions will be used by the CEC to determine whether the events listed below constitute a device or procedure related serious adverse event included in the primary endpoint. Most of the definitions have been adapted from the 2017 HRS/EHRA/ECAS/APHS/SOLAECE Expert Consensus on AF Ablation [17].

Primary Safety Event	Description
Atrioesophageal fistula	A connection between the atrium and the lumen of the esophagus. Evidence supporting this diagnosis includes documentation of esophageal erosion combined with evidence of a fistulous connection to the atrium, such as air emboli, an embolic event, or direct observation at the time of surgical repair. A CT scan or MRI scan is the most common method of documentation of an atrio-esophageal fistula.
Bleeding	Bleeding is a major complication of AF ablation if it requires and/or is treated with transfusion or results in a 20% or greater fall in hematocrit.
Cardiac tamponade/perforation	The development of a significant pericardial effusion during or within 30 days of undergoing an AF ablation procedure. A significant pericardial effusion is one that results in hemodynamic compromise, requires elective or urgent pericardiocentesis, or results in a 1-cm or more pericardial effusion as documented by echocardiography. Cardiac tamponade/perforation should also be classified as "early" or "late" depending on whether it is diagnosed during or following initial discharge from the hospital.
Death	Adverse event resulting in the patient's death.
Heart block (AV block)	New, persistent 2 nd or 3 rd degree AV block not attributable to a vasovagal reaction or medication effect and requiring permanent pacing.
Myocardial infarction	Irreversible necrosis of heart muscle secondary to prolonged ischemia with at least one of the following three criteria: 
 
1. Detection of ECG changes indicative of new ischemia (new ST-T wave changes or new LBBB) that persist for more than 1 hour;
 
2. Development of new pathological Q waves on an ECG;
 
3. Imaging evidence of new loss of viable myocardium or new regional wall motion abnormality.
 

Pericarditis	Pericarditis should be considered a major complication following ablation if it results in an effusion that leads to hemodynamic compromise or requires pericardiocentesis, prolongs hospitalization by more than 48 hours, requires hospitalization, or persists for more than 30 days following the ablation procedure.
Phrenic nerve injury resulting in diaphragmatic paralysis	Phrenic nerve paralysis is defined as absent phrenic nerve function as assessed by a sniff test. A phrenic nerve paralysis is considered to be permanent when it is documented to be present 12 months or longer following ablation.
Pulmonary edema	Excess fluid in the lungs that includes all of the following: 
 
• Symptoms (e.g. dyspnea)
 
• Physical findings (e.g. rales, hypoxemia)
 
• Radiologic findings
 
• Response to diuretic therapy
 
• Requires hospitalization
 

Pulmonary vein stenosis	Reduction of the diameter of a pulmonary vein or a pulmonary vein branch of $\geq 70\%$ confirmed via imaging (CT or MRI).
Stroke / cerebrovascular accident	Stroke diagnostic criteria: 
 
• Rapid onset of a focal or global neurological deficit with at least one of the following: change in level of consciousness, hemiplegia, numbness or sensory loss affecting one side of the body, dysphasia or aphasia, hemianopia, amaurosis fugax, or other neurological signs or symptoms consistent with stroke
 
• Duration of a focal or global neurological deficit <math>\geq 24</math> hours; OR <math>< 24</math> hours if therapeutic intervention(s) were performed (e.g. thrombolytic therapy or
 

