### 4.0 ENDPOINTS

#### 4.1 Primary Endpoints and Rationale

##### 4.1.1 Primary Safety Endpoint

The primary safety endpoint is the rate of device and/or procedure-related serious adverse events with onset within 7-days of any ablation procedure that uses the TactiFlex SE catheter (initial or repeat procedure performed 31-80 days of initial procedure) that are defined below:

- Atrio-esophageal fistula
- Cardiac tamponade/perforation
- Death
- Heart block
- Myocardial infarction
- Pericarditis
- Phrenic nerve injury resulting in diaphragmatic paralysis
- Pulmonary edema
- Pulmonary vein stenosis
- Stroke/cerebrovascular accident
- Thromboembolism
- Transient ischemic attack
- Vagal nerve injury/gastroparesis
- Vascular access complications (including major bleeding events)

. Atrio-esophageal fistula, cardiac tamponade/perforation and pulmonary vein stenosis will be evaluated through 12-months.

. Bleeding is a major complication of AF ablation if it requires and/or is treated with transfusion or results in a 20% or greater fall in hematocrit.

These events must meet the criteria listed in **Appendix II** to be included in the primary endpoint as adjudicated by the Clinical Events Committee (CEC).

The performance goal for the Primary Safety Endpoint for this clinical trial

= 12.9%.

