### 4.1.1.1 Rationale for Selection of the Primary Safety Endpoint

Peri-procedural serious adverse events (SAEs) that are adjudicated as being related to the procedure and/or the device are being assessed in the primary safety endpoint. The majority of the pre-identified SAEs that require reporting in this study occur within the first 7-days following an ablation procedure. It has become industry standard to report adverse events with onset within the first 7-days of an ablation procedure for AF. However, symptoms of PV stenosis and atrial-esophageal fistula may not be apparent in the acute period following the procedure. Notably, the 2004 FDA Guidance entitled "Clinical Study Designs for Percutaneous Catheter Ablation for Treatment of Atrial Fibrillation", dated January 9, 2004 [32] recommends that PV stenosis be assessed at 3-months and 1-year post-ablation. Additionally, cardiac tamponade/perforation may be related to the device/ procedure even though it may not be discovered within the 7-day post-procedure period. Therefore, symptoms indicative of PV stenosis, atrial-esophageal fistula, and cardiac tamponade/perforation be assessed throughout the clinical investigation and appropriate follow-up testing be conducted as clinically indicated.

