### **6.6.4 Repeat Ablation Procedures**

One ablation procedure is allowed during the blanking period (between 31 and 80 days post-initial procedure) due to AF/AFL/AT recurrence without being considered an effectiveness endpoint failure. The repeat procedure must be performed with the TactiFlex SE catheter using the recommended parameters listed in the *Instructions for Use* document and in **Section 6.3**. The TactiFlex SE catheter cannot be used for repeat procedures that occur  $\geq 81$  days after the initial procedure or if the subject requires a third ablation procedure at any time during the follow-up period (a marketed ablation catheter should be used).

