2.3 Endpoint Analysis

2.3.1 Primary Endpoints

2.3.1.1 Primary Safety Endpoint

The primary safety endpoint is the rate of device and/or procedure-related serious adverse events with onset within 7-days of any ablation procedure that uses the TactiFlex SE catheter (initial or repeat procedure performed 31-80 days of initial procedure).

The primary safety endpoint hypothesis is stated as follows:

$$H_0: P_S \geq [REDACTED]$$

$$H_a: P_S < [REDACTED]$$

where P_S is the percentage of subjects with a primary safety endpoint event and [REDACTED] is the performance goal. [REDACTED]

Events will be adjudicated by the Clinical Events Committee (CEC).

Statistical Analysis Plan

[REDACTED]

[REDACTED]

[REDACTED]

The primary effectiveness endpoint rate will be calculated using the Kaplan-Meier method based on the primary effectiveness analysis population. [REDACTED]

[REDACTED]

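### The primary safety endpoint evaluates tamponade/perforation through 12 months, but the definition an event must meet stops 30 days after an ablation

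*Protocol*

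**What the plan says.** Protocol 4.1.1 defines the primary safety endpoint as listed device- or procedure-related serious adverse events with onset within 7 days of any ablation using the study catheter. Footnote 1 makes an exception for three events: "Atrio-esophageal fistula, cardiac tamponade/perforation and pulmonary vein stenosis will be evaluated through 12-months". The CIP summary (Appendix X) and SAP 1.4.1.1 repeat this footnote.

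Protocol 4.1.1.1 gives the reason. It says that "cardiac tamponade/perforation may be related to the device/ procedure even though it may not be discovered within the 7-day post-procedure period", and that symptoms of the three conditions are to "be assessed throughout the clinical investigation and appropriate follow-up testing be conducted as clinically indicated".

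Section 4.1.1 then requires events to meet the Appendix II criteria "to be included in the primary endpoint as adjudicated by the Clinical Events Committee (CEC"). Appendix II confirms its role: "The following definitions will be used by the CEC to determine whether the events listed below constitute" an event belonging to the primary endpoint. Its entry for cardiac tamponade/perforation reads "The development of a significant pericardial effusion during or within 30 days of undergoing an AF ablation procedure". The entries for atrio-esophageal fistula and pulmonary vein stenosis contain no time limit.

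**The concern.** The same event has two windows, and the plan does not say which governs. Footnote 1 qualifies a sentence about onset, so its natural reading is that a related tamponade with onset at any time up to 12 months counts. The Clinical Events Committee, however, is bound to a definition that requires the effusion to have developed by day 30 after an ablation.

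This is one of the two endpoints that must both succeed under Protocol 8.11, in a single-arm trial tested against a fixed goal of 12.9%. The two texts give different numerators. The one that binds the committee is narrower, so any difference lowers the observed rate and makes the goal easier to meet. Late related events would still appear in the descriptive adverse event data through 12 months (Protocol 4.4), so they are not hidden, but they would not enter the test.

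**Working it through.** **Passages side by side, for the three events under footnote 1**

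| Event | Endpoint window (4.1.1, Appendix X, SAP 1.4.1.1) | Time limit in Appendix II |
|---|---|---|
| Atrio-esophageal fistula | 12 months | none |
| Pulmonary vein stenosis | 12 months | none |
| Cardiac tamponade/perforation | 12 months | 30 days from an AF ablation |

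Only tamponade/perforation is in conflict, so a general drafting convention does not explain it.

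**Length of the gap.** Follow-up runs 12 months from the initial procedure (Protocol 3.0), taken here as 365 days.

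- No repeat procedure: the Appendix II window closes on day 30. The gap is days 31 to 365, which is 335/365 = 92% of follow-up.
- With a repeat: Protocol 6.6.4 states that "One ablation procedure is allowed during the blanking period (between 31 and 80 days post-initial procedure"). The last 30-day window then closes between day 31 + 30 = 61 and day 80 + 30 = 110. At least 365 − 110 = 255 days remain in conflict, or 255/365 = 70%.

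An effusion that developed by day 30 and was found later can satisfy both texts. One that developed later cannot.

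**Effect on the rate.** SAP 2.3.1.1 defines the tested quantity: it "is the percentage of subjects with a primary safety endpoint event". Only a subject with no other qualifying event therefore matters. One such subject is 1/305 = 0.33 percentage points at the enrolled main-study N, and 1/285 = 0.35 at an assumed evaluable N of 285.

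**Effect on the verdict.** The test, alpha and evaluable N are redacted, so there is no plan figure to reproduce. Assume an exact one-sided binomial test. The pass limit is the largest x with P(X ≤ x | N, 0.129) ≤ alpha, equivalently a Clopper-Pearson one-sided upper bound below 12.9%.

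| N | Alpha | Pass limit | Observed rate | Upper bound at limit | Upper bound at limit + 1 |
|---|---|---|---|---|---|
| 305 | 2.5% | 27 | 8.85% | 12.62% | 12.99% |
| 305 | 5% | 29 | 9.51% | 12.74% | 13.10% |
| 285 | 2.5% | 25 | 8.77% | 12.68% | 13.08% |
| 285 | 5% | 27 | 9.47% | 12.83% | 13.22% |

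Excluding one subject changes the verdict only if the remaining count sits exactly on the limit. That probability is P(X = limit) with X ~ Binomial(N, r), for assumed true rates r:

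| N, alpha | r = 5% | 6% | 7% | 8% | 9% |
|---|---|---|---|---|---|
| 305, 2.5% | 0.16% | 1.2% | 3.8% | 6.9% | 8.0% |
| 305, 5% | 0.04% | 0.4% | 2.0% | 5.0% | 7.4% |
| 285, 2.5% | 0.25% | 1.5% | 4.4% | 7.4% | 8.3% |
| 285, 5% | 0.07% | 0.6% | 2.4% | 5.4% | 7.7% |

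All of these are conditional on one such subject existing. The unconditional chance is lower, and the documents give no rate from which to compute it.

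**Related gap in data collection.** The 12-month visit (6.6.3) prompts only for pulmonary vein stenosis symptoms, and the tamponade row of Table 4 is blank in the 12-month column. The 3-month, 12-month and unscheduled visits have no fistula prompt. Adverse events are collected at every visit, so this is secondary.

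**The case against.** The strongest counter-reading is that the two texts do different jobs: footnote 1 sets how long subjects are followed, and Appendix II is a case definition. Section 4.1.1.1 speaks of late discovery rather than late development, and Appendix II itself classes tamponade as early or late by when it is diagnosed. On that view the effusion must develop by day 30 and may be found at any time up to month 12. This reading is possible, but no visible passage states it, and it fits poorly with a footnote that makes an exception to an onset window. If it is what the sponsor means, one sentence would settle the matter.

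Several limits do stand:

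- Text after the endpoint definition and after its rationale, SAP Appendix A and the derivation of the safety goal are redacted, and the committee's charter is not available. Any of these might resolve the question. The conflict is established for the visible text only.
- If the 12.9% goal was built on a 30-day definition, applying Appendix II would be the like-for-like comparison. A narrower numerator lowers the rate in either case, but whether that makes the comparison unfair cannot be judged here.
- The true rates of 6% to 9% lie near the pass limit. At 5% and N=305 the conditional probability falls to 0.16% or less.
- Missing symptom prompts do not mean that late events go uncollected.

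**Conclusion.** The concern holds, with high confidence as to the wording. Followed literally, the plan counts a related tamponade developing more than 30 days after the most recent ablation under one passage and rejects it under another that is mandatory. The gap covers 70% to 92% of follow-up.

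The numerical effect is probably small: 0.33 to 0.35 percentage points per affected subject, and about a 0.4% to 8% chance that one such subject changes the verdict. That range rests on an assumed exact one-sided test, alpha of 2.5% or 5%, N of 305 or 285, and true rates of 6% to 9%. It should be fixed because it leaves the numerator of a decisive endpoint undefined and because a change made after event timing is known would not be credible.

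**What to change.** Before any adjudication, reconcile Protocol 4.1.1, 4.1.1.1, Appendix II and Appendix X with SAP 1.4.1.1, so that one tamponade/perforation window governs the endpoint, the committee's definition and the analysis. Either lift the 30-day limit in Appendix II for primary-endpoint purposes or correct the 12-month statements. The choice is the sponsor's and should match how the 12.9% goal was derived. State whether the window refers to onset or diagnosis, and from which procedure it runs when there is a repeat. Check that SAP Appendix A and the committee's charter agree.

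Report the safety rate under the other window as a sensitivity analysis. As a minor item, reconcile the symptom prompts at the 3-month, 12-month and unscheduled visits, and the 12-month column of Table 4, with 4.1.1.1.

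The cost is one definition or footnote edit, two document checks and a few visit-form prompts. If the 12-month window is kept, a few more events may count against the goal.
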